# **8.2.3.1** Statistical Methods for Efficacy Analyses

# Phase A (Week 0 to Week 52)

The primary efficacy analyses will compare the efficacy of ertugliflozin relative to glimepiride in change from baseline in A1C at Week 52. The mean change from baseline in A1C at Week 52 in the ertugliflozin 15 mg group will be compared to that in the glimepiride group using the estimated treatment difference via a constrained longitudinal data analysis (cLDA) model, proposed by Liang and Zeger [15]. This cLDA model assumes a common mean across treatment groups at baseline and a different mean for each treatment at each of the post-baseline time points. In this model, the response vector consists of baseline values and the values observed at each post-baseline time point. The cLDA model will include terms for treatment, time, prior antihyperglycemic medication (monotherapy or dual therapy), baseline eGFR, and the interaction of time by treatment. Time will be treated as a categorical variable so that no restriction is imposed on the trajectory of the means over time. The treatment difference in terms of mean change from baseline to a given time point will be estimated and tested from this model. Ertugliflozin 15 mg will be declared non-inferior to glimepiride in terms of A1C reduction if the upper limit of the two-sided 95% confidence interval (CI) for the mean difference between ertugliflozin 15 mg and glimepiride at Week 52 is less than the non-inferiority margin,  $\delta$ =0.3%. This margin was chosen because changes from baseline smaller than -0.3% have limited clinical impact, and the 0.3% margin balances lesser clinical impact with a study sample size that is feasible to conduct. The non-inferiority test for ertugliflozin 5 mg in A1C reduction will use the same approach described above following the multiplicity control strategy in Section 8.2.5. If non-inferiority is declared for ertugliflozin 15 mg, then an assessment of superiority will be conducted following the multiplicity control strategy described in Section 8.2.5. For the cLDA model, the Kenward-Roger adjustment will be used with restricted (or residual) maximum likelihood (REML) to make proper statistical inference. An unstructured covariance matrix will be used to model the correlation among repeated measurements and hence avoids the potential bias that could result from the use of specific structured covariance models. If the unstructured covariance model fails to converge with the default Newton-Raphson algorithm, the Fisher scoring algorithm or other appropriate methods can be used to provide initial values of the covariance parameters. In the rare event that none of the above methods yield convergence, a structured covariance such as Toeplitz can be used to model the correlation among repeated measurements. In this case, the empirical option will be used because the sandwich variance estimator is asymptotically unbiased while the model-based variance estimator can substantially overestimate or underestimate the true variance. The cLDA model uses the maximum likelihood principle to estimate the parameters and account for missing data in an implicit fashion. Values of eGFR that are >120 mL/min/1.73 m^2 will be set to 120  $mL/min/1.73 m^2$ .

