
**Protocol/Amendment No.:** 002-01

Although the baseline measurement is included in the response vector, it is independent of treatment, and hence, the baseline means are constrained to be the same for different treatment groups. Of note, in the event that there are no missing data, the estimated treatment difference from the above cLDA model will be identical to that from a traditional longitudinal analysis of covariance (ANCOVA) model which uses the baseline value as a covariate. However, unlike longitudinal ANCOVA, the cLDA model accounts for variability in the baseline values, thus providing more accurate standard errors and CIs for individual treatment effects. Moreover, this model allows the inclusion of subjects who are missing either the baseline or post-baseline measurements, thereby increasing efficiency. An example of SAS implementation code is given in Section 12.8.

All other continuous efficacy endpoints will be analyzed using the above cLDA method described for A1C

An analysis of covariance (ANCOVA) model will be used in the PP population as sensitivity analyses for the primary and key secondary efficacy endpoints at Week 52. The ANCOVA model will include treatment, prior antihyperglycemic medication, baseline eGFR, and baseline value. By definition, there will be no missing outcome data in the PP population.

The ANCOVA model as described above will also be used in the FAS population for the primary and key secondary efficacy endpoints. The last-observation-carried-forward (LOCF) method will be used to impute missing data.

If the size of the mFAS population (described in Section 8.2.2.1) differs from the size of the FAS by >2% in any treatment group, primary and key secondary endpoints will be analyzed in the mFAS population using the same cLDA methodology described for the FAS.

All continuous efficacy endpoints will be summarized and plotted over time by treatment group.

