For the analysis of percentages of subjects at the A1C goals of <7.0% and <6.5% at Week 52, the constrained longitudinal data analysis (cLDA) model that is used for the analysis of A1C will be used to impute the missing data for A1C. Imputations of the missing data will be based on the marginal univariate normal distributions with means equal to the predicted values and variances equal to the squared standard errors for the predicted values from the cLDA model. Ten sets of imputations of each missing value will be constructed from the cLDA model. The seed for the random number generator will be 8835002. Observed data will not be imputed. Subjects will be categorized as at or not at the A1C goals (<7.0% or <6.5%) at Week 52 after imputation. An additional analysis of the percentages of subjects at A1C goals will treat all subjects with missing Week 52 data as not being at goal, regardless of the final observed A1C value.

To estimate the odds ratio, each of the 10 imputed data sets will be analyzed by logistic regression. The logistic regression model will include terms for treatment and baseline A1C. Parameter estimates on log odds ratio will be combined using standard multiple imputation techniques proposed by Rubin [20] to yield an overall estimate of log odds ratio. Log odds ratio will be back transformed into odds ratio for final reporting.

**Protocol/Amendment No.:** 002-01

A time-to-rescue analysis will also be performed. The proportion of subjects rescued in each treatment group will be summarized. Plots of the Kaplan-Meier estimate of the distribution of the time-to-rescue will be provided for each treatment arm and log-rank tests comparing the time-to-rescue distribution of ertugliflozin at a specific dose level versus glimepiride will be conducted. In this analysis, subjects will be censored at the time of discontinuation.

To assess the overall benefit of the trial treatment, the proportion of subjects meeting the composite endpoint of an A1C decrease >0.5% with no AE of symptomatic hypoglycemia and no weight gain by the end of Week 52 will be analyzed using the M&N method in the FAS population for both A1C and body weight at Week 52 [16]. Additionally, the proportion of subjects with an A1C < 7% with no symptomatic hypoglycemia at Week 52 will be analyzed using the same MN method in the FAS population for A1C. For both composite endpoints, missing data will be imputed via the LOCF method.

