# 8.2.7 Subgroup Analyses and Effect of Baseline Factors

To assess whether the treatment effect at Week 52 is consistent across various subgroups, the estimate of the between-group treatment effect (with a nominal 95% CI) for the primary endpoint will be estimated and plotted within each category of the following classification variables:

- Baseline A1C levels: by categories: <8.0%; ≥8.0%
- Age categories:  $\leq$  or > median age
- Gender (female; male)
- Race (White, Black, Asian, Other)
- Ethnicity (Hispanic or Latino, Not Hispanic or Latino)
- BMI ( $\leq$  or > median)
- Prior antihyperglycemic therapy (monotherapy or dual therapy)
- Time since diagnosis of Diabetes ( $\leq$  or > median years)

For the subgroups that have only 2 categories, if the sample size is not at least 20 subjects in all of the treatment groups in each subgroup category, then that subgroup analysis will not be performed. For the race subgroup analysis, if the sample size is not at least 20 subjects in all of the treatment groups in a certain race category, then that race will be combined with the "Other" race category. The consistency of the treatment effect will be assessed in the context of a repeated measures ANCOVA (RMANCOVA) method, which is a generalization of the standard ANCOVA to accommodate repeated measurements. The RMANCOVA model will adjust for baseline value for A1C, treatment, baseline eGFR, subgroup, and treatment-bysubgroup interaction. Time is treated as a categorical variable and time-specific versions of each term listed above at each week will be used to acknowledge the repeated nature of the measurements. An unstructured covariance matrix will be used to model the correlation among repeated measurements. For subgroup analyses based on factors that are already in the main model, the respective term will appear in the model only once. Treatment effects and nominal 95% confidence intervals by category for the classification variables listed above will be reported as well as presented graphically. Formal statistical testing of treatment-by-subgroup interactions will not be performed.

**Protocol/Amendment No.:** 002-01

The treatment effect across trial centers will be summarized for A1C at Week 52 with descriptive statistics.

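### The A1C-goal logistic model omits prior therapy and baseline eGFR, which the other A1C models use; the analysis is valid but gives up a little power

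*Combined protocol and SAP*

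**What the plan says.** Section 8.2.3.1 gives the primary cLDA model terms for treatment and time together with "prior antihyperglycemic medication (monotherapy or dual therapy), baseline eGFR, and the interaction of time by treatment". It sets eGFR values above 120 mL/min/1.73 m² to 120. The sensitivity analyses follow the same pattern: "The ANCOVA model will include treatment, prior antihyperglycemic medication, baseline eGFR, and baseline value".

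For the A1C-goal proportions, missing values are filled in from the same cLDA: the "model that is used for the analysis of A1C will be used to impute the missing data for A1C". Ten imputed data sets are then analysed by logistic regression, and here the list is shorter: "The logistic regression model will include terms for treatment and baseline A1C".

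Section 8.2.7 defines the subgroup model for the primary endpoint: "The RMANCOVA model will adjust for baseline value for A1C, treatment, baseline eGFR, subgroup, and treatment-bysubgroup interaction". Baseline eGFR is there and prior medication is not. Prior therapy is, however, one of the eight subgroup factors, so it enters that one analysis as the subgroup term. The section adds: "For subgroup analyses based on factors that are already in the main model, the respective term will appear in the model only once".

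**The concern.** The same laboratory measurement is analysed with different covariate sets, and the plan does not say why. Two features suggest an oversight. The summary of changes explains that eGFR was brought into the models because renal function may affect the efficacy of a drug that acts on the kidney, and that reasoning applies equally to A1C goal attainment. The plan also uses both covariates to impute A1C and then leaves them out when it analyses the imputed values.

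Prior therapy could carry information beyond baseline A1C. Under Table 1, dual-therapy subjects are screened at 6.5 to 8.5% and come off an agent for at least 8 weeks (10 after a sulfonylurea) before a 2-week run-in, so at least 10 to 12 weeks in all. Section 4.2.3.1 says that A1C reflects the preceding 3 to 4 months. Their baseline value may therefore not have settled.

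At stake is some power for secondary objective 9, and for its Week 104 counterpart in objective 17.

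**Working it through.** **1. The plan's own figure.** The documents give no power for the logistic or subgroup model. The primary figure in Section 8.2.6 reproduces: with 337 effective subjects per arm, SD 1.0% and margin 0.3%, the standard error is √(2/337) = 0.0770. Power is Φ(0.3/0.0770 − 1.960) = Φ(1.93) = 97.3%, against 97% stated. It does not depend on the models discussed here.

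**2. Model terms side by side.**

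| Analysis of A1C | Baseline A1C | Prior medication | Baseline eGFR |
|---|---|---|---|
| Primary cLDA | in the response vector | yes | yes |
| Sensitivity ANCOVA | yes | yes | yes |
| A1C-goal logistic model | yes | no | no |
| Subgroup RMANCOVA | yes | only as the subgroup factor | yes |

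Prior antihyperglycemic agents are recorded on the eCRF (Section 7.1.1.5.1), and eGFR comes with the chemistry panel (Table 7).

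**3. Size, effects set on the log-odds scale.** Assumed: 410 per arm, complete data, true odds ratio 1.5, 30% on dual therapy, 1,500 simulated trials per row. Efficiency is [(ln OR / SE) with both covariates ÷ (ln OR / SE) as planned]².

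| Log-odds effect: prior therapy / eGFR per SD | Planned: OR, SE, power | Both added: OR, SE, power | Efficiency |
|---|---|---|---|
| 0 / 0 | 1.510, 0.154, 77.7% | 1.512, 0.154, 78.0% | 1.01 |
| −0.3 / 0.1 | 1.502, 0.154, 75.1% | 1.507, 0.155, 75.3% | 1.00 |
| −0.6 / 0.2 | 1.490, 0.153, 74.3% | 1.506, 0.156, 75.5% | 1.01 |
| −1.0 / 0.4 | 1.464, 0.152, 70.9% | 1.509, 0.158, 73.5% | 1.08 |

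For the last row: ln 1.464 / 0.152 = 2.508, ln 1.509 / 0.158 = 2.604, and (2.604/2.508)² = 1.08. The efficiencies come from rounded entries and are good to about 0.01. The last row is a deliberately strong case, since a log-odds effect of −1.0 is an odds ratio of 0.37. The power gains are 0.3, 0.2, 1.2 and 2.6 points. The first is simulation noise, because no covariate acts there.

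**4. Size, effects set on the A1C scale.** Assumed: 410 per arm, complete data, 35% on dual therapy, residual SD 0.85%, treatment difference 0.2%, 1,000 trials. Prior therapy shifts A1C by 0.2 to 0.3%, and eGFR by 0.1 to 0.2% per SD.

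- Smaller effects: SE rises from 0.1458 to 0.1473, efficiency is up 1.6%, power goes from 73.1% to 73.8%.
- Larger effects: SE rises from 0.1456 to 0.1497, efficiency is up 4.6%, power goes from 73.9% to 76.5%.

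In the larger case the SE grows by 0.1497/0.1456 = 1.028 while the test statistic grows by √1.046 = 1.023. The log odds ratio must therefore have grown by about 1.028 × 1.023 = 1.052. The larger estimate produces the gain, and the standard error works against it.

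**5. Validity.** With a true odds ratio of 1 (1,000 trials per setting of step 3), the upper-tail error was 2.2 to 2.4% for the planned model and 2.2 to 2.3% for the larger one, against 2.5% nominal.

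**The case against.** The case for leaving the model alone is respectable. The logistic model is pre-specified and unambiguous, so the analyst has no discretion. Objective 9 carries no hypothesis, the endpoint is listed among the other endpoints in Table 10, and Section 8.2.5 treats it as supportive at a nominal level. The size rests on assumed inputs: no section gives the dual-therapy share or any covariate effect, and the simulations ignore the 31.2% attrition assumed by Week 52 and the multiple imputation. All of this stands. It limits the point to a small improvement.

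A reader might infer four stronger things that the documents do not support.

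- *That the planned model loses precision.* In logistic regression, adding prognostic covariates raises the standard error of the treatment coefficient and moves the coefficient away from zero. The gain is in power only.
- *That the imputation and analysis models conflict.* An imputation model richer than the analysis model is acceptable. The troublesome direction is the reverse.
- *That the comparison is biased.* Section 5.4 uses no stratification, so no design factor is being left out, and step 5 shows no error-rate problem.
- *That the subgroup results are on the wrong basis and that one added term would align them with the primary model.* Only seven of the eight subgroup analyses lack prior medication, and no gain has been shown for them. The RMANCOVA also conditions on baseline A1C and uses time-specific terms, whereas the cLDA lists only a time-by-treatment interaction. The adjustment would come closer without matching. The sentence about entering a main-model factor only once may hint that prior medication was intended, but the listed terms do not include it.

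**Conclusion.** The point holds as a minor improvement. The A1C-goal logistic model omits two covariates that the plan already collects and already uses in its primary and sensitivity models for A1C. The analysis as planned is valid. Under effects assumed on the A1C scale, the omission costs about 0 to 5% in test efficiency; only the deliberately strong log-odds setting goes higher, to about 8%. In every setting the cost is 0 to about 3 points of power, and it is zero if neither covariate predicts A1C given baseline. These figures assume complete data and could differ under the planned attrition and imputation. Neither the primary conclusion nor any test in the multiplicity procedure is affected.

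**What to change.** In Section 8.2.3.1, add prior antihyperglycemic medication and baseline eGFR, capped at 120 mL/min/1.73 m², to the A1C-goal logistic model. Apply the same terms to the analysis that counts missing as not at goal and to the Week 104 analysis, and state that the odds ratio is conditional on these covariates as well as on baseline A1C. Otherwise, give the reason for the shorter list.

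Optionally, for consistency, add time-specific prior medication to the Section 8.2.7 model in the seven subgroup analyses where it is not already the subgroup factor, noting that this approaches the primary adjustment without reproducing it.

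The cost is a sentence in each section and two more model parameters in the logistic regression. No new data are needed. Section 8.2 says that no separate SAP will be issued, so the change belongs in this text and should be made before the Week 52 unblinding, so that the covariates cannot look chosen after the fact.

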### Management of Randomized Subjects

At Visit 4/Randomization (Day 1), subjects will enter the 104-week, double-blind, active-comparator-controlled treatment period and be randomized in a 1:1:1 ratio to ertugliflozin 5 mg once-daily (q.d.), ertugliflozin 15 mg q.d., or glimepiride. Glimepiride/matching placebo will be initiated at 1 mg q.d. and titrated up to the maximum approved dose (6 or 8 mg q.d. based on the local country label) or maximum tolerated dose. Glimepiride/matching placebo may be down-titrated to avoid or manage hypoglycemia (see Section 5.2.1.2 for detailed instructions about titrating glimepiride). Subjects are to remain on their stable dose of metformin (≥1500 mg/day) while receiving blinded investigational product during the double-blind treatment period.

During Phase A/Year 1, subjects who are on the maximum labeled dose or maximum tolerated dose of glimepiride/matching placebo for at least two weeks and who meet progressively more stringent glycemic rescue criteria (see Table 6) will initiate open-label sitagliptin glycemic rescue medication in accordance with the local country label. Subjects who are rescued in Phase A/Year 1 will not be eligible to enter Phase B/Year 2. The study design does not include glycemic rescue therapy in Phase B/Year 2. During Phase B/Year 2, subjects who are on the maximum labeled dose or maximum tolerated dose of glimepiride/matching placebo for at least two weeks and who meet glycemic criteria specified in Section 5.8 will be discontinued from treatment with blinded investigational product.

Subjects who are discontinued from blinded investigational product for any reason other than withdrawal of consent will be followed by telephone contacts for the duration of the trial according to the Trial Flow Chart - Section 6.0. The purpose of these telephone contacts, as well as the 14-day post trial telephone contact, will be to collect SAEs and events eligible for adjudication (see Section 7.3.4).

This trial is designed to evaluate, in adult subjects with T2DM and inadequate glycemic control on diet and exercise and metformin, the effect of both the 5 and 15 mg doses of ertugliflozin on glycemic control, symptomatic hypoglycemia, body weight, and blood pressure following a 52-week dosing period. It is also designed to evaluate the long-term efficacy, safety and tolerability of ertugliflozin during the entire 104-week double-blind, active-comparator-controlled treatment period.

[figure not shown]

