## The following objectives will be assessed for ertugliflozin 15 mg q.d. and 5 mg q.d.

*In subjects with T2DM and inadequate glycemic control on metformin, after 52 weeks* 

(8) **Objective:** To assess the effect of the addition of ertugliflozin compared with the addition of glimepiride on change in fasting plasma glucose (FPG) from baseline.

- (9) **Objective:** To assess the effect of the addition of ertugliflozin compared with the addition of glimepiride on the proportion of subjects at the A1C goal of <7.0% (<53 mmol/mol).
- (10) **Objective:** To assess the effect of the addition of ertugliflozin compared with the addition of glimepiride on the proportion of subjects who require rescue and the time to rescue.
- (11) **Objective:** To assess the effect of the addition of ertugliflozin compared with the addition of glimepiride on diastolic blood pressure.
- (12) **Objective:** To assess the effect of the addition of ertugliflozin compared with the addition of glimepiride on durability of glycemic efficacy.
- (13) **Objective:** To assess the effect of the addition of ertugliflozin compared with the addition of glimepiride on the proportion of subjects meeting the composite endpoint of an A1C decrease >0.5% with no symptomatic hypoglycemia and no body weight gain.
- (14) **Objective:** To assess the effect of the addition of ertugliflozin compared with the addition of glimepiride on the proportion of subjects meeting the composite endpoint of an A1C <7.0% with no symptomatic hypoglycemia
- (15) **Objective:** To assess the effect of the addition of ertugliflozin compared with the addition of glimepiride on lipid profile (including HDL-C, triglycerides, total cholesterol, LDL-C, and non-HDL-C cholesterol).
- (16) **Objective:** To assess the effect of the addition of ertugliflozin compared with the addition of glimepiride on HOMA-%β.

In subjects with T2DM and inadequate glycemic control on metformin, after 104 weeks

- (17) **Objective:** To assess the effects of the addition of ertugliflozin compared with the addition of glimepiride on A1C, FPG, and the proportion of subjects at the A1C goal of <7.0% (<53 mmol/mol).
- (18) **Objective:** To assess the effects of the addition of ertugliflozin compared with the addition of glimepiride on symptomatic hypoglycemia.
- (19) **Objective:** To assess the effects of the addition of ertugliflozin compared with the addition of glimepiride on change in body weight from baseline.

04T4BY

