- FPG consistently >240 mg/dL (13.3 mmol/L) after Visit 5/Week 6 through Visit 6/Week 12.
- FPG consistently >200 mg/dL (11.1 mmol/L) after Visit 6/Week 12 through Visit 8/Week 26.
- FPG consistently >200 mg/dL (11.1 mmol/L) or A1C >8.0% (64 mmol/mol) after Visit 8/Week 26

Phase B/Year 2: Subjects who have a repeated, confirmed FPG >200 mg/dL (11.1 mmol/L) or single A1C >8.0% without a reasonable explanation (e.g., intercurrent illness or medication omission) despite receiving a maximum labeled or maximum tolerated (if lower than maximum labeled) dose of glimepiride/matching placebo for at least two weeks.

**Note:** A consistent value for FPG is defined as a repeat measurement performed within 7 days of notification from the central laboratory. Site should reinforce diet/exercise counseling prior to repeat measurement.

- 3. Hypoglycemia: Repeated (2 or more episodes since the prior visit) FPG or fingerstick glucose
  - <50 mg/dL (2.8 mmol/L) with or without symptoms of hypoglycemia, or
  - ≤70 mg/dL (3.9 mmol/L) with symptoms of hypoglycemia, and without a reasonable explanation (e.g., increased physical activity or skipped meal) or with a reasonable explanation and likely to reoccur.

**Note:** Subjects should only be discontinued from blinded investigational product due to hypoglycemia after the subject has down-titrated and interrupted glimepiride/matching placebo (see Section 5.2.1.2.2). Subjects rescued with sitagliptin must first interrupt sitagliptin and if the subject continues to experience hypoglycemia, the dose of glimepiride/matching placebo should be down-titrated and if necessary interrupted. If the subject continues to experience hypoglycemia despite interruption of glimepiride/matching placebo, all blinded investigational product should be discontinued.

04T4BY Confidential

Protocol/Amendment No.: 002-01

4. Abnormal liver function tests meeting criteria specified below (see Section 12.5 for additional details on management and discontinuation of blinded investigational product for subjects with elevated liver enzymes).

- o ALT or AST  $\ge 3X$  ULN with total bilirubin (TBL)  $\ge 2X$  ULN and alkaline phosphatase (ALP) < 2X ULN and without an established etiology; or
- o ALT or AST ≥8X ULN or ≥3X ULN with symptoms consistent with liver injury and without an established etiology; or
- ALT or AST  $\geq$ 5X ULN for 2 weeks or longer; or

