#### OR

eGFR consistently <45 mL/min/1.73 m^2 (MDRD formula).

**Note:** A consistent value is defined as a repeat measurement performed within 7 days of notification from the central laboratory. If the eGFR or serum creatinine value continues to meet discontinuation criteria but demonstrates stability or improvement relative to the prior result, an additional repeat may be performed (within 7 days). If this repeat continues to meet the discontinuation criteria, the subject must be discontinued. See Section 7.1.5.9 for guidance on following subjects who discontinue blinded investigational product due to decreased renal function or renal-related adverse events.

- 6. Requirement for one of the prohibited medications listed in Section 5.1.3
- 7. Subjects have been rescued or who meet the threshold for glycemic rescue medication and have a known hypersensitivity or intolerance to sitagliptin.

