# 7.1.1.8.7 Dispense Open-Label Sitagliptin Rescue Medication (if applicable)

Subjects who meet progressively more stringent glycemic thresholds (see Section 5.6) and have been on the maximum labeled dose (6 or 8 mg q.d.) or on a maximum tolerated dose of glimepiride/matching placebo for at least two weeks will be dispensed open-label sitagliptin at the rescue visit through Visit 9/Week 39.

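### Time to rescue censors never-rescued subjects who meet the Phase A threshold but cannot take sitagliptin, and does not say how to count those who first meet it at Visit 10

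*Combined protocol and SAP*

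**What the plan says.** Secondary objective 10 (Section 3.2), a 52-week objective, concerns "the proportion of subjects who require rescue and the time to rescue". Section 8.2.3.1, under the Phase A heading, specifies Kaplan-Meier curves and log-rank tests of each ertugliflozin dose against glimepiride. Section 8.2.2.1 sets the population as All Subjects Treated. On events, Section 8.2.3.1 says "The proportion of subjects rescued in each treatment group will be summarized". On censoring, it says "In this analysis, subjects will be censored at the time of discontinuation".

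The passages that decide who can become an event are these:

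- **Section 5.6:** a subject with a history of hypersensitivity or intolerance to sitagliptin is taken off blinded product. Rescued subjects otherwise stay on it.
- **Section 5.8, criterion 7:** discontinuation covers subjects who "meet the threshold for glycemic rescue medication and have a known hypersensitivity or intolerance to sitagliptin". It also covers subjects already rescued.
- **Section 5.8, criterion 2, Phase A:** hyperglycemia discontinuation applies only after at least 4 weeks of sitagliptin rescue.
- **Section 7.1.1.8.7:** subjects who qualify "will be dispensed open-label sitagliptin at the rescue visit through Visit 9/Week 39".
- **Section 6.0:** the row for assessing potential rescue or discontinuation is marked at Visit 10/Week 52. The row for dispensing rescue medication stops at Visit 9.
- **Section 2.1:** "The study design does not include glycemic rescue therapy in Phase B/Year 2".

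**The concern.** The objective is about requiring rescue, while the analysis counts receiving it. The protocol makes these two groups differ. A subject who meets the threshold and cannot take sitagliptin is removed because of glycemic failure and then enters the curve as censored. Kaplan-Meier and log-rank methods assume that censoring carries no information about the event. For this subject, the reason for censoring is that the event condition was met. The missing-at-random argument in Section 8.2.3.1 concerns the cLDA likelihood and does not carry over to an unadjusted log-rank test.

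A second gap lies at the end of Year 1. A subject whose first qualifying result is the Visit 10 sample meets a Phase A threshold, but the documents do not say whether that subject is rescued, or how the analysis counts a subject who is not.

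At stake are the estimated proportion requiring rescue and the shape of the rescue curve for a supportive endpoint.

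**Working it through.** The plan gives no event rate, event count or power for time to rescue, so there is no stated figure to reproduce. The check traces each route by which a subject can meet the threshold.

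**1. Phase A hyperglycemia discontinuation (Section 5.8, criterion 2).** At least 4 weeks of sitagliptin must come first. Starting sitagliptin is the event, so it precedes discontinuation and later censoring cannot remove it. None are lost.

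**2. Phase A threshold met, sitagliptin not possible, never rescued (Section 5.6; Section 5.8, criterion 7).** The subject is discontinued and censored, although rescue was required. To size this, assume that a fraction r of an arm meets the threshold and a fraction i of those cannot take sitagliptin. Neither rate is in the documents. The number lost per arm is 410 × r × i.

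| r (assumed) | i (assumed) | Lost per arm | Crude proportion counted, r × (1 − i) |
|---|---|---|---|
| 3% | 0.5% | 410 × 0.03 × 0.005 = 0.06 | 2.98% |
| 10% | 1% | 410 × 0.10 × 0.01 = 0.41 | 9.9% |
| 20% | 3% | 410 × 0.20 × 0.03 = 2.46 | 19.4% |

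If i is the same in two arms, both proportions shrink by the same factor (1 − i). Their ratio is then unchanged, and their difference shrinks by at most 3% of its size in this range.

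**3. Threshold first met at Visit 10/Week 52.** The last row of Table 6 starts after Week 26 and has no end within Year 1, so an A1C above 8.0% at Week 52 meets it. The preceding scheduled A1C is at Week 39, 13 weeks earlier. Assessment is marked at Visit 10, dispensing ends at Visit 9, and Phase B has no rescue. The documents give no rate for subjects who first cross at this visit, so the number cannot be derived.

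**4. Phase B.** Criterion 2 discontinues "Subjects who have a repeated, confirmed FPG >200 mg/dL (11.1 mmol/L) or single A1C >8.0% without a reasonable explanation", with the dose condition met. The cut-offs are numerically those of Table 6 after Week 26. No rescue event can occur in this period. Whether that matters depends on the analysis window:

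- Objective 10 is a Week 52 objective, Table 11 applies at Week 52 unless it says otherwise, and the Week 104 section covers only endpoints collected at Week 104.
- Section 8.2.3 nevertheless calls for between-group comparisons of all efficacy endpoints in Phase A and in Phase A + Phase B. Table 10 lists time to rescue as an efficacy endpoint.

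If a 104-week curve were produced, suppose that 10% are rescued in Year 1, that a fraction f of those entering Year 2 meet the criterion, and that there is no other loss (all assumed). The written rule gives 10.0% at Week 104. Counting those failures gives 1 − 0.90 × (1 − f), which is 14.5%, 19.0% or 28.0% for f = 5%, 10% or 20%.

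**The case against.** The strongest case against the point is that little is lost. The main Year 1 route to glycemic discontinuation runs through rescue, so those events are counted. Criterion 7 partly covers subjects already rescued, who are also counted. What remains is a handful of subjects in a supportive endpoint outside the multiplicity procedure. All of this stands, and it limits the size of the point.

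On Visit 10, the flow-chart row combines rescue and discontinuation, so its mark does not promise rescue at that visit. A subject who completes Week 52 unrescued can be seen as ordinary end-of-period censoring. There is also some monitoring between Visits 9 and 10: a Week 45 telephone contact, instructions to report high fingerstick values, and rescue at unscheduled visits. This is a fair reading, but the plan does not state it, and Section 8.2.3.1 sets no administrative censoring date.

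A reader might infer two stronger claims that the documents do not support. The first is that glycemic discontinuations in general are turned into non-events. Section 5.8 rules this out for Phase A hyperglycemia discontinuations by requiring prior sitagliptin. The second is that Year 2 glycemic failures go uncounted in the trial. Objective 10 ends at Week 52, and rescue is absent from the 104-week objectives. Reasons for discontinuation are displayed (Section 8.2.4), missingness is accounted for in detail (Section 8.2.3.1), and the proportion below A1C 7.0% is carried to Week 104.

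Replacing time to rescue altogether with a glycemic-failure endpoint would be a preference, not the correction of an error.

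**Conclusion.** The point holds in a narrow form. The written rule censors never-rescued subjects who meet the Phase A threshold and are discontinued because they cannot take sitagliptin. That conflicts with the wording of objective 10 and makes the censoring informative. The size is probably 0 to 3 subjects per arm, resting on the assumed 3% to 20% meeting the threshold and 0.5% to 3% unable to take sitagliptin. The plan also leaves unclear how subjects who first meet the threshold at Visit 10 are counted, and that number cannot be sized from the documents. The time window is not stated firmly enough to exclude a Phase A + Phase B curve that would be flat after Week 52 by construction. Primary and key secondary conclusions do not depend on any of this. The change is worth making because it is cheap and removes a bias that the rule itself creates.

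**What to change.** In Section 8.2.3.1 and Table 11:

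1. Define the event as initiation of sitagliptin, or discontinuation without rescue after meeting the applicable Section 5.6 threshold, whichever comes first. Censor only other discontinuations.
2. State that time to rescue covers Phase A, with administrative censoring at its end.
3. If a Phase A + Phase B analysis is produced, label it a supplementary time to glycemic failure that counts Phase A rescue plus Phase B discontinuation under the Section 5.8 hyperglycemia criterion.
4. Also report the number of subjects who actually started sitagliptin.

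Separately, reconcile the Visit 10 assessment mark in Section 6.0 with the dispensing row and Section 7.1.1.8.7. Then state how a threshold first met at that visit enters the analysis.

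The cost is SAP wording and one derived variable from laboratory and disposition data already collected. The derivation needs a disposition record that identifies criterion 7 discontinuations, because the threshold also depends on a repeat FPG and on the two-week dose condition. The downside is an event slightly broader than sitagliptin use, which item 4 addresses.
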